APPROVAL LETTER/NOTICE NOTE: List all items (verbatim) that you want to be included in your approval letter (e.g., Amendment date, Investigator's Brochure version, consent form(s) version(s), advertisement name, etc.) in the box below.

By checking this box, I verify that I, as the Protocol Director (PD) responsible for this research protocol, have read and agree to abide by the above obligations, or that I have been delegated authority by the PD to certify that the PD has read and agrees to abide by the above obligations.

Statistical Analysis Plan

In testing Hypotheses 1 and 2, treatment response will be evaluated in terms of improvement in the Insomnia Severity Index (ISI) from baseline to end of the 6-week treatment.

Primary Hypothesis 1: Efficacy of CBT-I compared to a manualized active control condition, Arousal Based Therapy for Insomnia (ABT-I). To test the hypothesis that CBT-I will show efficacy for insomnia in TBI patients at the end of the 6-week treatment period, compared to the control condition (ABT-I) we will regress change in ISI on treatment (CBT-I versus ABT-I; 6 weeks vs. baseline). We will run analogous models to test for persistent treatment effects at the 16 and 24-week follow-up points. In each set of models the dependent variable will first be the change relative to baseline in our primary outcome measure of insomnia change defined by the ISI scores. We will covary for comorbid PTSD severity and amount of medication use (SSRIs) as required, if the frequency of such differs by treatment group.

Secondary Hypothesis 2: Moderators and Mediators of response. Our previous design separated Sleep Restriction (SR) and Cognitive Therapy (CT) components of CBT-I, however, we feel that although the design of the study has been changed, we can still gather some preliminary data on likely moderators and mediators of CBT-I, SR and CT while conducting the clinical trial and testing our Primary Hypothesis. Thus, we can still determine whether changes in potential moderators and mediators of SR and CT might also moderate or mediate the effects of the entire CBT-I package.

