Exploratory analyses will compare the predictive usefulness of all measures listed in Table 5. In more detail, we will fit regression models for change in ISI on treatment, the continuous moderator and the treatment by moderator interaction. Baseline Medication use and PTSD should be similar across groups due to randomization and use of the blocking procedures (Section 2.a.3.b.5). The analysis may be adjusted for other covariates (age and alcohol use) if they are significantly different between groups at baseline despite randomization. We will use percentile, bootstrap confidence intervals to determine the moderator value, if any, at which there is a change in the optimal choice of treatment (i.e. the point of intersection at which one treatment first surpasses another). Our results will allow us to choose the optimal treatment based on individual moderator values and estimate the comparative advantage of one treatment over another given a specific moderator value. The confidence intervals will also show the moderator values, if any, for which the difference between treatments is statistically or clinically insignificant.

Secondary Hypothesis 2: Mechanisms of Action (Mediators). As in the case of moderators of treatment response, since our design has changed mediators of treatment response are reduced in prominence in this proposal. Nonetheless, we feel some exploratory analyses may be carried out. For example, we hypothesize that changes in TIB with its associated increase in homeostatic pressure for sleep may account for some of the effects of SR and that changes in measures of worry and pain may explain some of the effects of CT. In the package of combined SR plus CT (CBT-I) this may still be the case for the group as a whole. Therefore, we will conduct secondary analyses using the bootstrap strategy for mediator analysis formulated by Preacher and Hayes [98] to address this possibility. Specifically, we will fit three separate regression models to estimate the indirect effect of treatment through the mediator: 1) Change in ISI on treatment; 2) Change in mediator on treatment; and 3) Change in ISI on treatment plus change in mediator. Each model will be adjusted for the same covariates described above. We will estimate the indirect effect as the product of the treatment effect in (2) and the mediator

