effect in (3). We will compare the indirect effect to the total effect of treatment, estimated in (1), to determine how much of the total effect of treatment is accounted for by the mediator. Due to the non-normality of the estimates, percentile bootstrap confidence intervals for the mediator effects will be computed and their statistical significance assessed. We propose to use multiple imputation [99, 100] and an analyses based on total ISI change over the course of the study. Additional mediator analyses will be performed for relevant measures listed in Table 5.

Likelihood of Obtaining Useful Results. For our primary hypothesis we considered a target power of 80% with a two-tailed test at 5% significance in an Intention-to-Treat (ITT) analysis. We will require 60 subjects per group (for a total of 120 in the two groups) to detect a main effect of treatment group with an effect size that increases R-squared by 6% or more, with respect to the continuous outcome variable (ISI improvement). Thus we feel that the sample of 60 per group is adequate. Power analyses were computed using G*Power Version 3.1.9.2 [101].

Considerations Regarding Sleep Medication Changes During the Study. Tentatively, we would consider patients who required a sleep medication increase a treatment failure and they would be scored accordingly. We would interpret a decrease in medications a sign that therapy was working and assume that the ISI ratings would reflect a treatment success. We plan to monitor these assumptions with our statistical team and adjust our analyses appropriately.

Other analyses. The above is meant to be a brief outline of our analytic approach. Other analyses will be conducted including examination of secondary outcomes such as Quality of Life measures.

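### The ISI change models leave out baseline ISI, a precision loss worth between nothing and about 14 points of 6-week power that one covariate would recover

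*Combined protocol and SAP*

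**What the plan says.** Under Primary Hypothesis 1 the SAP states: "we will regress change in ISI on treatment (CBT-I versus ABT-I; 6 weeks vs. baseline". It continues: "We will run analogous models to test for persistent treatment effects at the 16 and 24-week follow-up points". Two sets of covariates are named, and both are conditional. For the primary models: "We will covary for comorbid PTSD severity and amount of medication use (SSRIs) as required, if the frequency of such differs by treatment group". In the moderator section: "The analysis may be adjusted for other covariates (age and alcohol use) if they are significantly different between groups at baseline despite randomization". Baseline ISI is in neither set.

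The three mediator regressions under Mechanisms of Action include "2) Change in mediator on treatment" and carry the rule "Each model will be adjusted for the same covariates described above". Baseline ISI is therefore absent there too.

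The power statement (Likelihood of Obtaining Useful Results) aims for 80% power, two-sided 5%, with 60 per group and an "effect size that increases R-squared by 6% or more". It gives no ISI standard deviation, no baseline to follow-up correlation and no dropout allowance.

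**The concern.** Taking change as the outcome is not the same as adjusting for baseline. It fixes the slope of follow-up ISI on baseline ISI at 1 instead of estimating it. If the true slope is different, part of the baseline variation stays in the residual, the confidence interval for the treatment effect is wider than it need be, and power falls. Baseline ISI must already be collected to form the outcome, so the information is there and unused.

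A chance baseline difference between arms shifts the unadjusted estimate by (1 − slope) times that difference. That is the same loss seen conditionally on the imbalance, not a further cost.

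The point concerns the three ISI outcome models first. A moderator model may already contain baseline ISI, because protocol section 1b lists insomnia severity as a possible moderator, so the moderator models are not counted as an omission.

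**Working it through.** **Inputs from the SAP.** N = 120 (60 per arm), two-sided alpha 0.05, R-squared 0.06, treatment as sole predictor.

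**Assumed inputs (not in the documents).** Baseline to follow-up correlation ρ from 0.3 to 0.8; SD ratio k = follow-up SD / baseline SD from 1.0 to 1.5; 120 complete ISI pairs.

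**Step 1: the plan's own figure.** f² = 0.06/0.94 = 0.0638. The noncentrality is λ = 120 × 0.0638 = 7.66. With the noncentral F on 1 and 118 df, power is 78.4%, close to the stated 80%; exactly 80% needs N = 125 in total. If the 6% is an increment over other predictors that explain a further 5% (assumed), f² = 0.06/0.89, λ = 8.09 and power is 80.5%.

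**Step 2: variance with and without baseline ISI.** With the baseline SD set to 1:

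- change score: 1 + k² − 2ρk
- baseline-adjusted: k²(1 − ρ²)
- slope: ρk
- difference of the two variances: (1 − slope)²

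At ρ = 0.3, k = 1 these are 1.40 and 0.91, and the difference is 0.49 = (1 − 0.3)². The difference is zero only at slope 1.

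**Step 3: power with baseline ISI.** Multiply λ by V = (1 + k² − 2ρk) / [k²(1 − ρ²)] and use 117 residual df. The lost degree of freedom costs less than 0.01 points by itself (78.379% to 78.373%).

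| k | ρ = 0.3 | 0.5 | 0.6 | 0.7 | 0.8 |
|---|---|---|---|---|---|
| 1.0 | 92.6% | 88.7% | 86.6% | 84.5% | 82.5% |
| 1.3 | 86.4% | 82.0% | 80.1% | 78.7% | 78.5% |
| 1.5 | 83.7% | 79.8% | 78.7% | 78.5% | 80.3% |

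- Maximum, ρ = 0.3, k = 1.0: V = 1.40/0.91 = 1.538, λ = 11.78, power 92.6%. The interval width ratio is √(1/1.538) = 0.81, so it is 19% narrower.
- Minimum, ρ = 0.8, k = 1.25 (slope 1): V = 0.5625/0.5625 = 1, power 78.4%.

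The slope alone does not fix the gain. At slope 0.5, power is 94.0%, 88.7%, 84.5% and 82.9% for k = 0.8, 1.0, 1.3 and 1.5.

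**Step 4: chance imbalance.** The figures above ignore the small cost of estimating the slope when the arms differ at baseline by chance. Multiplying λ by (1 − 1/118) gives 78.0% to 92.4%. Simulation of 40,000 trials at each extreme gives 77.9% and 92.1%.

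**Step 5: other assumptions.**

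- At k = 0.8 (follow-up less variable than baseline), power is 92.9% to 97.2%.
- With 96 complete pairs (assumed 20% loss), 68.8% becomes 68.8% to 86.0%.
- The SAP would count participants who need more sleep medication as failures but does not define their score. Assuming that improvement is set to 0 for a random 10% (6,000 simulated trials, Monte Carlo error about 0.6 points), power goes from 70.4% to 82.9% at ρ = 0.3, k = 1, and from 69.9% to 69.4% at ρ = 0.8, k = 1.25.

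No gain is computed for weeks 16 and 24, because the documents give no effect size there.

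**Step 6: mediator models.** The SAP compares the indirect effect with the total effect. If baseline ISI were added only to the two models with ISI change as outcome, total would no longer equal direct plus indirect. Apart from sign, the gap is (mediator effect) × (baseline coefficient in the mediator model) × (baseline mean difference). With 60 per arm that difference has SD √(2/60) = 0.183 baseline SDs, so assumed coefficients of 0.3 and 0.3 give a typical gap of 0.3 × 0.3 × 0.183 = 0.016. With baseline ISI in all three models the gap vanishes.

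**The case against.** The strongest reply is that nothing in the plan is wrong. Response is defined as ISI improvement, the regression tests that, and the sample size is set on the same outcome. A more efficient model is an option, not a correction. This stands as to validity, and the point is put only as lost precision.

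The size of the benefit is assumed. The 92.6% is a corner of the grid. With equal weight on each grid point (ρ and k in steps of 0.01) the median gain is 3.8 points and 61% of points gain less than 5. These are shares of an assumed grid, not probabilities, but they show that the top of the range should not be read as typical. Near slope 1, adjustment can cost about 0.4 points once chance imbalance is allowed for. The 78.4% is one reading of the 6%; the other reading gives 80.5%, which meets the target. All of this stands as a limit on size. It does not argue for omission, since the worst case is a few tenths of a point.

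The SAP calls itself a brief outline and refers to a Table 5 and a section on blocking that are not in the available text. Baseline ISI might appear there. But the SAP does list its covariates, and nothing available puts baseline ISI in the primary model.

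Finally, it may be too late. The protocol's Resources section expected completion by the end of 2023, and the approval period runs to 07/31/2025. If outcomes by arm have been seen, a sensitivity analysis will not raise the power of the primary test. This also stands.

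**Conclusion.** The concern holds. The 6-, 16- and 24-week ISI models omit baseline ISI, and adding it at 6 weeks would move power from 78.4% to between 78.4% and 92.6% (about 78.0% to 92.4% with chance imbalance allowed for), with an interval 0 to 19% narrower. This rests on 120 complete pairs, 6% read as the R-squared of treatment alone, and the assumed ranges for correlation and SD ratio; the gain is nil at slope 1 and larger if the follow-up SD is below the baseline SD. Fewer complete pairs are possible: section 9e, item 6 excludes some participants with serious adverse events from analysis, and no dropout allowance is stated. It is a change that should be made, not one on which the trial's validity depends. Confidence in its size is medium.

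**What to change.** Before outcomes by arm are seen, pre-specify baseline ISI as an unconditional covariate in the 6-, 16- and 24-week models. The change outcome can stay: once baseline ISI is in the model, the treatment estimate is identical to that with follow-up ISI as outcome. If baseline ISI is carried into the mediator analysis, put it in all three regressions, including the one for change in the mediator; this keeps the SAP's same-covariates rule and the decomposition intact. Add it to any moderator model that does not already contain it.

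The cost is 1 degree of freedom per model, no new data and a dated SAP change. If outcomes by arm have already been seen, keep the planned model as primary and report the adjusted one as a labelled sensitivity analysis.

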The Berlin Questionnaire will be used to screen for sleep apnea symptoms, and the Duke Structured Interview will be used to screen for both symptoms of both Obstructive Sleep Apnea and Periodic Limb Movement Disorder. Participants who are determined to be at high risk for these disorders will be referred to Pulmonary Medicine for further evaluation.

Summary Research Team Meeting and Sleep Disorders Diagnosis:

Before a subject will be entered into the treatment, the summary research team will review all aspects of the case to determine ultimate eligibility. All evidence collected during the screening will be used to develop formal sleep disorders diagnoses.

BASELINE

Two Weeks of Baseline Sleep Logs:

At the end of the first screening session, participants will be shown how to complete daily sleep logs for the duration of the study to provide subjective sleep data. We will use a modified Consensus Sleep Diary-E for our sleep log. Sleep logs will be returned to us during in person visits, or via MyHealtheVet.

Baseline Evaluation:

In this session subjects will complete psychological evaluations. Cognitive testing will be administered on paper and using the CANTAB Connect Research software via iPad. A blood sample will be collected at this visit.

Optional Polysomnography (PSG):

Participants who agree will be set up with a Compumedics Siesta

Title : Non-Pharmacological Treatments for Insomnia in Chronic Traumatic Brain Injury
Approval Period: 07/31/2024 - 07/31/2025

ambulatory overnight PSG recording at the end of their baseline evaluation. Participants will then return home to sleep, and return the next morning to provide urine and blood samples. VA approved taxi and hotel service may be offered for those traveling long distances or who don't have a ride to and from the VA for the PSG.

Blood and Urine samples:
Urine samples will be collected at baseline, eight-week and six-month visits for all participants. Urine samples will be screened by the PAVAHCS laboratory for several exclusionary medications and drugs, and results will be uploaded to the participant's secure medical file.

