\$50 for the baseline visit, and a further \$50 if they choose to participate in the overnight sleep study & blood/urine test.
\$25 for each of the 6 treatment visits.
\$50 for the end-of-treatment visit, and a further \$50 if they choose to participate in the overnight sleep study & urine test.
\$50 for the 6-month follow up visit, and a further \$50 if they choose to participate in the overnight sleep study & blood/urine test.

In-person participants will receive \$10 VA canteen lunch vouchers for the longer screening, baseline and follow up visits.

If it is necessary for a participant to terminate before the end of follow-up because of the return of symptoms, they will be paid for the portion of the study they have completed.

We feel this is a reasonable amount in light of the time and effort the participant will spend in the study. The amount of this payment is similar to that paid for by other labs conducting similar studies.

I) Costs. Please explain any costs that will be charged to the participant.

No costs to the subject will arise as a result of participation in this study, other than transportation to and from the Center, and the time involved.

m) Estimate the probable duration of the entire study. Also estimate the total time per participant for: (i) screening of participant; (ii) active participation in study; (iii) analysis of participant data.

The entire study should take 4 years.

- (i) Screening for each participant will take approximately 2-3 hours
- (ii) Each participant will actively participate in the study for approximately 32 weeks.
- (iii) Analysis of participant data is estimated to take about 6-12 months.

9. Risks

a) For the following categories include a scientific estimate of the frequency, severity, and reversibility of potential risks. Wherever possible, include statistical incidence of complications and the mortality rate of proposed procedures. Where there has been insufficient time to accumulate significant data on risk, a statement to this effect should be included. (In describing these risks in the consent form to the participant it is helpful to use comparisons which are meaningful to persons unfamiliar with medical terminology.)

i. The risks of the Investigational devices.

Not applicable.

ii. The risks of the Investigational drugs. Information about risks can often be found in the Investigator's brochure.

Not applicable.

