The Protocol Director will review all Adverse Events and Serious Adverse Events as soon as possible after the occurrence. SAEs are reported and forwarded to IRB as appropriate.

Title : Non-Pharmacological Treatments for Insomnia in Chronic Traumatic Brain Injury
Approval Period: 07/31/2024 - 07/31/2025

5. If applicable, how frequently will the Monitoring Committee meet? Will the Monitoring Committee provide written recommendations about continuing the study to the Sponsor and IRB?

Information about adverse events is collected at each visit by the interviewer. Any potentially serious problem is brought immediately to the Protocol Director. All data entered into the database is monitored by the senior research associate and the database manager.

6. Specify triggers or stopping rules that will dictate when the study will end, or when some action is required. If you specified this in Section 2g [Study Endpoints], earlier in this application enter 'See 2g'.

Criteria for discontinuation of a patient in the study will include an increase in bothersome nightmares for a week under treatment. We have not seen consistent reporting of nightmares with the proposed treatments, however that is always possible, hence again we would want to make sure that that occurred for at least a week before a patient was discontinued. Patients will be allowed to continue in the protocol after an SAE independent of treatment, e.g. hospitalization following a fall. All treatments are considered active and patients will be allowed to continue their treatment as a courtesy. However, data from such subjects will not be included in statistical analyses since such SAEs may affect sleep. Patients will not be restarted if their sleep deteriorates meeting the above criteria and they are discontinued from the protocol.

7. Indicate to whom the data and safety monitoring person, board, or committee will disseminate the outcome of the review(s), e.g., to the IRB, the study sponsor, the investigator, or other officials, as appropriate.

Serious Adverse Events are reported to the IRB using the standard reporting forms.

8. Select One:

The Protocol Director will be the only monitoring entity for this study.
 This protocol will utilize a board, committee, or safety monitor as identified in question #2 above.

10. Benefits

a) **Describe the potential benefit(s) to be gained by the participants or by the acquisition of important knowledge which may benefit future participants, etc.**

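### The SAP assigns no missing-data method to the primary or follow-up ISI models, so the intention-to-treat analysis is undefined and would by default use only participants with a follow-up ISI

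*Combined protocol and SAP*

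**What the plan says.** **Primary model.** Under Primary Hypothesis 1 the SAP states: "we will regress change in ISI on treatment (CBT-I versus ABT-I; 6 weeks vs. baseline". The same form of model is planned at 16 and 24 weeks. No method for missing ISI scores is given for any of the three.

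**Imputation.** The one reference is in the SAP's mediator section: "We propose to use multiple imputation [99, 100] and an analyses based on total ISI change over the course of the study". It stands between the bootstrap intervals for mediator effects and a sentence on further mediator analyses.

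**Analysis population.** Intention-to-treat is named once, in the power paragraph: "we considered a target power of 80% with a two-tailed test at 5% significance in an Intention-to-Treat (ITT) analysis".

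**Stopping.** Section 9e item 6 makes a week of increased bothersome nightmares a ground for discontinuation and adds: "Patients will not be restarted if their sleep deteriorates meeting the above criteria and they are discontinued from the protocol". Section 8k, on payment, foresees that a participant may "terminate before the end of follow-up because of the return of symptoms". Neither place says whether the ISI is still collected.

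**Other analysis rules.** Section 9e item 6 also removes from the statistical analyses the data of participants who have a serious adverse event independent of treatment. The SAP's paragraph on sleep medication tentatively scores a medication increase as treatment failure and gives no ISI value for it.

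**Data that could inform imputation.** Section 2a has participants "complete daily sleep logs for the duration of the study".

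**The concern.** A change score needs both ISI values. Without the later one the participant has no outcome, and ordinary regression software leaves that person out. The written plan therefore gives the exploratory analysis an imputation method and the primary analysis none, although the primary analysis is the one described as intention-to-treat.

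Two things are at stake. First, if leaving is related to response and the pattern differs between arms, the completers no longer form a randomised comparison. Sleep restriction is part of CBT-I only, and Section 9a(iv) says it may make participants very sleepy. Control participants who do not improve may also leave. Bias in either direction is plausible. Second, if the method is left open until the data are seen, the handling of missing scores can be chosen with the result in view.

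**Working it through.** **1. The plan's own figure.** Inputs from the SAP's power paragraph: two-sided 5%, 80% power, R-squared increase 0.06, 60 per group.
- f² = 0.06/0.94 = 0.0638. Noncentrality = f² × N = 0.0638 × 120 = 7.66.
- The F test with 1 tested predictor gives 78.4% power at N = 120; 80% needs N = 125.
- If covariates explain a further 4% of variance (assumption), f² = 0.06/0.90 = 0.0667 and N = 120 exactly.

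So the figure reproduces closely. The equivalent standardised difference without covariates is d = 2 × √0.0638 = 0.505. Section 8a plans to enrol 120, the same number, which leaves no allowance for loss.

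**2. Power on completers** (loss rates assumed; same formula at 120 × (1 − loss), no covariates):

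| Loss | N analysed | Power |
|---|---|---|
| 0% | 120 | 78.4% |
| 10% | 108 | 74.0% |
| 15% | 102 | 71.5% |
| 20% | 96 | 68.8% |
| 30% | 84 | 62.9% |

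**3. Bias when loss depends on early response.** Simulation with 60 per arm and ISI improvement in SD units. Early sleep-log response is correlated 0.6 with improvement (assumed), and loss is logistic in early response. There is no true effect, and only completers are analysed. A positive sign favours CBT-I.

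| Loss, CBT-I v ABT-I | Who leaves | Bias (SD) | Type I error |
|---|---|---|---|
| 25% v 10% | poor responders, mainly in CBT-I | about +0.14 | about 10% |
| 25% v 10% | poor responders, same link in both arms | about +0.09 to +0.10 | 7-8% |
| 10% v 25% | poor responders, mainly in ABT-I | about -0.14 | not tabulated |
| 20% v 20% | same link in both arms | about 0 | about 5% |
| 20% v 20% | selective in CBT-I only | about +0.13 | about 10% |

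Hand check of the error rates: 25% and 10% loss leave 45 and 54 participants, so SE = √(1/45 + 1/54) = 0.202. A bias of 0.10 is 0.10/0.202 = 0.50 SE, which gives two-sided rejection of 7.9%. A bias of 0.14 is 0.69 SE and gives 10.7%. Both agree with the simulation to within about a percentage point.

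Multiple imputation using the early log gave bias of about 0 and type I error of 4.7-5.6%. That result is built in, because loss was made to depend on the variable used for imputation.

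**4. Bias when loss depends on the unseen ISI change.** Suppose a latent tendency to leave has correlation −ρ with improvement and a fraction p leaves. The completer mean then shifts by ρ × φ(z)/(1 − p), with z the 1 − p normal quantile. The ratio φ(z)/(1 − p) is 0.195, 0.274, 0.424 and 0.497 for p = 10%, 15%, 25% and 30%. With true d = 0.505:
- 25% v 15%: 0.505 + ρ × (0.424 − 0.274), which is 0.55 at ρ = 0.3 and 0.58 at ρ = 0.5.
- 30% v 10%: 0.505 + ρ × (0.497 − 0.195), which is 0.60 and 0.66.
- 15% v 25%: 0.46 and 0.43.
- Equal loss with equal ρ: no shift.

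Standard imputation assumes the data are missing at random and would not by itself remove this bias.

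**The case against.** The strongest reply is that the SAP never says participants without a follow-up ISI are dropped. It claims intention-to-treat, it calls itself a brief outline, and its imputation sentence concerns total ISI change rather than a mediator, so the sentence may be meant more widely. This stands in part. A reader might infer that the SAP prescribes a complete-case primary analysis. It does not: that is the default of the model, and the documents leave the method unspecified. But total change over the study is not the 6-week change of the primary model, and being an outline does not supply the missing method.

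The evidence for outcome-related loss is also limited. The deterioration wording in Section 9e refers back to the nightmare criterion, and the same item says nightmares have not been consistently reported with these treatments. The return-of-symptoms text in Section 8k concerns payment and bears mainly on later follow-up, less on the 6-week endpoint. Stopping treatment is not the same as missing an ISI. Section 2a sets sleep schedules with participant input, and Section 9a(iv) ties its precautions to the first days of therapy. All of this stands: the documents make outcome-related loss possible, but they do not show that it will be large.

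Finally, the value of the logs is uncertain. The correlation of 0.6 has no source in the documents. Logs come back at visits or by secure messaging, so early leavers may supply few.

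**Conclusion.** The gap is real and worth closing before analysis. No missing-data method is assigned to the primary 6-week ISI model or to the 16- and 24-week models, so the intention-to-treat analysis is undefined and by default would use completers only.

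The size of the effect is unknown because the documents give no loss rate. Under the assumed 25% v 10% loss and correlation of 0.6, complete-case bias is about +0.10 to +0.14 SD with type I error of 8-10% if CBT-I loses more poor responders. It is about -0.14 SD if ABT-I does, and about 0 if loss and selection are equal. Equal loss rates alone are not a safeguard if selection differs between arms.

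A reader might conclude that the bias favours CBT-I. The documents do not support a direction: that result needs poor responders to leave mainly or more often from CBT-I, and the mirror case shrinks the estimate by a similar amount. Nor do they support the view that imputation alone settles the matter, since that depends on data missing at random. The clearest written conflict with intention-to-treat is the exclusion in Section 9e item 6 of participants with a serious adverse event independent of treatment.

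**What to change.** In Primary Hypothesis 1 of the SAP:
1. State that the 6-, 16- and 24-week ISI models include all randomised participants. Use multiple imputation by arm, with baseline ISI, ISI at the other visits and available sleep-log averages in the imputation model. A likelihood-based repeated-measures model is an acceptable alternative.
2. Add one sensitivity analysis that shifts the imputed ISI by a stated delta, in both arms, for participants who left early.
3. State that the ISI is still requested at scheduled visits after treatment stops, unless consent is withdrawn. Name the visits: Section 2a places the outcome measures at week 8 and six months, while the SAP analyses 6, 16 and 24 weeks.
4. Reconcile the all-randomised population with the exclusion in Section 9e item 6, and with the tentative scoring of a sleep-medication increase as failure, so that each such participant has one defined outcome value.

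The cost is SAP wording and some programming. The method is already named in the SAP, and the ISI and logs are already collected; only the ISI requests after stopping may add data collection. Where loss is unrelated to arm, imputation can have slightly less power than complete-case analysis: 69% v 73% in one simulated scenario with 20% loss per arm.
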